PROTOCOL

(Version April 2015)

TRIGR

Trial to Reduce IDDM in the Genetically at Risk

RESEARCH DESIGN AND METHODS

This is a randomized double blinded intervention study using an intention to treat statistical analysis to compare the incidence of predictive autoantibodies and clinical diabetes in the two treatment groups.

A. STUDY POPULATION

Newborn infants who have a first degree relative (FDR) with type 1 diabetes (i.e. a mother, father or full sibling), and who meet the inclusion but not the exclusion criteria are recruited:

Inclusion criteria:

1. The biological parent and/or full (not half) sibling of the newborn infant has type 1 diabetes as defined by the World Health Organization
2. The infant's parent or legal guardians give signed consent to participate

Exclusion criteria:

1. An older sibling of the newborn infant has been included in the TRIGR intervention
2. Multiple gestation
3. The parents are unwilling or unable to feed the infant cow's milk (CM) based products for any reason (e.g., religious, cultural).
4. The newborn infant has a recognizable severe illness such as those due to chromosomal abnormality, congenital malformation, respiratory failure needing assisted ventilation, enzyme deficiencies, etc.
5. The gestational age of the newborn infant is less than 35 weeks
6. Inability of the family to take part in the study (e.g. the family has no access to any of the Study Centers, the family has no telephone)
7. The infant has received any infant formula other than Nutramigen prior to randomization
8. The infant is older than 7 days at randomization
9. No HLA sample drawn before the age of 8 days

B. SAMPLE SIZE

The sample size estimation presented in Table 1 is based on experiences from family studies analyzing the occurrence of autoantibodies in siblings of children with type 1 diabetes or in offspring of affected parents and progression to clinical disease in such young first-degree relatives. The data on the frequency of multiple (≥ 2) autoantibodies by the age of 6 years and the cumulative incidence of type 1 diabetes by the age of 10 years are based on 82 young siblings from the DiMe Study carrying increased genetic risk for type 1 diabetes as defined according to the criteria in the Pilot-2 trial (106).

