All statistical analyses will be based upon the total cohort of subjects randomized into the trial. Although data on some subjects may be missing at points in time, all relevant data available from each subject will be employed in the analyses. In all principal analyses, subjects will be included in the group

to which they were initially assigned and this assignment will not be altered based on a subject's adherence to the assigned treatment program. Analyses of each outcome will include an assessment of possible differences among clinical centers. Baseline variables that will be used in stratified analyses include gender, HLA risk category and other prognostic characteristics. If differences in baseline characteristics are observed, analyses will be conducted of the effects of the treatments on outcomes adjusting for the potential confounding effects of these baseline characteristics. If only a few such baseline characteristics are identified, analyses will be conducted stratifying for those characteristics. If any more than a few baseline characteristics are identified, because of small sample size, it will be necessary that regression models be employed to adjust the treatment comparison for the confounding effects of those characteristics. A number of subgroup analyses are planned to help identify individuals more likely to benefit from, or to be harmed by, the treatment. In regard to treatment effects, definition of such subgroups will rely on baseline data, not data measured after randomization. Such subgroups might include: gender, gender of the relative with type 1 diabetes, HLA risk group and other factors suspected to be associated with the event. Exploratory data derived through subgroup analyses will serve primarily to generate new hypotheses for subsequent testing, and conclusions drawn from subgroup hypotheses not explicitly stated before data analysis will have less credibility than those from hypotheses stated in the protocol. For safety monitoring, the Data Management Unit also will perform any and all analyses that are appropriate to identify subgroups that may be at significantly increased safety risk. The Kaplan-Meier method will be used to construct survival curves and the logrank statistic used to compare treatment arms with respect to time until the development of autoimmunity or type 1 diabetes.

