Randomization takes place before birth or immediately after the birth of the child. The research assistant or investigator obtains the formula allocation code from the Data Management Unit (DMU) by completing the Randomization Form electronically. Subjects who meet the inclusion and do not meet exclusion criteria are randomized as follows: randomization in each strata will be within four blocks. Subjects will receive either the test formula, casein hydrolysate (Nutramigen™, Mead Johnson Nutritionals), not containing antigenic CM protein, or a CM protein containing control formula which has an addition (20 %) of Nutramigen, whenever breast milk is not available. Any subject requiring supplemental feeding prior to randomization (e.g. infants born at night or on weekends) is given banked breast milk or Nutramigen. The randomization code will be kept by the manufacturer and it will be opened when TRIGR study is completed.

Cord blood is obtained from newborn infants whenever possible or alternatively a heel prick is performed to obtain capillary blood as soon as possible after birth, at the latest at the age of 7 days. The blood sample is forwarded to the continental genotyping center and screening performed for the presence of the genotypes listed below indicating an increased genetic risk. Results are entered into the Central Data Base immediately when available (within 2 weeks after the sampling) and are sent by e-mail from DMU to the national coordinating centers and/or to the local study center in question and to the Study Monitors. Only subjects with these genotypes are included in the nutritional prevention trial; all other subjects are withdrawn from the study at that time; their parents are told that genetic screening suggests that their child does not fall into the increased genetic risk group for type 1 diabetes and they are appropriately thanked for their participation. It is emphasized that their child might still develop diabetes despite not meeting the eligibility criteria.

E. GENETIC SCREENING

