and the outcome variables (e.g., the status of the diabetes-associated antibodies). At every time point the single antibody variable will be dichotomized as negative or positive, and a summary variable will be produced (negative if less than two variables are antibody positive and positive if two or more variables are antibody positive). The exposure to formula vs. placebo will be included in the model as an indicator variable. Age at initiation, duration of breast feeding and/or formula use and cumulative formula dose will be included in the model as potential effect modifying and confounding factors. The presence of interactions will be tested and the possible effect of the components considered will be estimated.

Two different statistical methods will be used to analyze the hypothesis that weaning to a casein hydrolysate decreases the occurrence of diabetes-associated antibodies. First, generalized linear models will be fitted to the data (20). Also random effect models will be used (21). These models which represent a general approach to the problem of modeling repeated measurements with fairly general error structures, can allow for missing observations, serial correlations, time-varying covariates, and irregular measurement occasions. Second, for the description of the data, the association of covariates with the risk of an elevated antibody at a given point of time will be assessed using logistic regression models (22). A rather similar statistical approach was used in the DCCT Study (23).

The analyses of the second hypothesis will use the time of diagnosis of manifest type 1 diabetes as the only outcome measure. The dataset will thus be similar to that of a cohort study, and the statistical analyses will be carried out using the proportional hazards regression model (24) including the milk exposure as the risk factor and potential confounding factors a covariates in the model. Also time-dependent covariates can be included to assess the effects of potential modifying factors. The adjusted relative risk of type 1 diabetes between the two groups of milk exposure will be estimated. Also the adjusted incidence of the disease in the two groups can be assessed.

M. INTERIM ANALYSIS

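### The autoantibody model must include feeding variables that arise after randomisation, so its arm coefficient need not be the intention-to-treat effect, and nothing says whether it or the logrank test decides

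*Combined protocol and SAP*

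**What the plan says.** Section L (Statistical methods) sets out two hypotheses. This point concerns the first, on diabetes-associated autoantibodies, where a child counts as positive with two or more positive antibodies.

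- On treatment: "The exposure to formula vs. placebo will be included in the model as an indicator variable". The term used is exposure, not assignment.
- On feeding: "Age at initiation, duration of breast feeding and/or formula use and cumulative formula dose will be included in the model". These variables enter as possible confounders and effect modifiers.
- On interactions: "The presence of interactions will be tested and the possible effect of the components considered will be estimated".
- On method: generalized linear models and random effect models are given for analysing the hypothesis. Only the logistic regression is confined to describing the data.

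Other sections bear on the same comparison.

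- The opening of Research Design and Methods describes a trial "using an intention to treat statistical analysis to compare the incidence of predictive autoantibodies and clinical diabetes in the two treatment groups".
- The analysis paragraph in section B, after Table 1, says: "In all principal analyses, subjects will be included in the group" first assigned, whatever the adherence. If baseline differences are seen, it plans analyses "adjusting for the potential confounding effects of these baseline characteristics". It bases subgroups for treatment effects on baseline data and excludes data collected after randomisation. It also plans Kaplan-Meier curves, with "the logrank statistic used to compare treatment arms with respect to time until the development of autoimmunity or type 1 diabetes".
- Section D gives the timing: "Randomization takes place before birth or immediately after the birth of the child".
- Section G leaves breast feeding to the mother.

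**The concern.** A confounder of a randomised comparison must precede allocation. Age at starting formula, feeding durations and cumulative dose follow it. Conditioning on them can do two things. It can remove part of an effect that acts through feeding. It can also link the arm to unmeasured family factors that influence both feeding and autoimmunity. In either case the coefficient answers a different question from the one the design poses.

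The plan also holds at least two analyses of one hypothesis with no order between them. If feeding differs by arm, the assigned-arm logrank test and the feeding-conditional model can disagree, and the choice between them could be made after the results are known. The and/or in the covariate list leaves open which duration enters, and in some situations that changes the answer. Section M lets the code be opened on an autoantibody result without naming the test that result comes from.

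**Working it through.** **1. Timing.** Allocation is before or just after birth (section D). Age at initiation, durations and cumulative dose accumulate over the intervention period of 6 to 8 months (section G). All are post-randomisation, except for any interim feed given before a postnatal allocation.

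**2. Which analysis the sample size fits.** Table 1 gives 1200 for two or more autoantibodies (9.9% by age 6, 40% effect, column I).

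- Events (Freedman): (1.960 + 0.842)² × (1.6/0.4)² = 7.849 × 16 = 125.6.
- Control hazard: −ln(1 − 0.099)/6 = 0.01737 per year. The treated hazard is 0.6 times that.
- Assume uniform accrual over 4 years, so follow-up runs from 6 to 10 years. The event probabilities are then 0.1296 and 0.0800, mean 0.1048.
- N = 125.6/0.1048 = 1199, against 1200 stated.

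The same method gives 1723 against 1735 for diabetes (7.6% by age 10). A two-proportion formula gives 1458, or 1558 with continuity correction. Table 1 therefore fits an unadjusted logrank-type comparison.

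**3. Effect of the feeding covariates: illustration only.** The arm shifts below are assumed.

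Model: U is an unmeasured family factor, B breast-feeding duration, A age at initiation, F formula-use duration and D cumulative dose, each with within-arm SD 1. The outcome is logit P(two or more antibodies by age 6) = a + ln(OR_U)·U, with no arm effect, and a set for 9.9% or 20.7% positive (both from Table 1). A = 0.7B + error and F = −0.7B + error. D = −0.7B + error, except where U also acts on dose directly; there D = −0.5B − 0.5ρU + error, with ρ the within-arm |corr(U,D)|. Each fit enters arm, A, D and one duration (F or B), which covers both readings of and/or. N = 2032, 5% Wald test, 4,000 trials per cell (1,000 in the sixth row).

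| Assumed situation, true null | Adjusted arm OR | False positives |
|---|---|---|
| No arm difference in feeding | same as unadjusted | 4.5–5.4% |
| 0.25 SD shift, ρ = 0.3, OR_U = 1.5 | 1.00 to 0.96 | 4.9–6.3% |
| 0.5 SD shift in D, OR_U = 2.0, U acts through B only, B entered | 1.00–1.01 | 5.2–5.4% |
| Same, F entered in place of B | 0.94 | 6.8–9.1% |
| 0.5 SD shift in D, OR_U = 2.0, U also acts on D | 0.90–0.92 | 8.6–13.8% |
| 0.5 SD shift in B, OR_U = 2.0, corr(U,B) = 0.4 | 0.87–0.91 | about 11–21% |
| 0.5 SD shift in B, OR_U = 2.0, corr(U,B) = 0.57 | 0.83–0.87 | 15.7–39.2% |

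The unadjusted arm test stays at 4.3–6.0%. Reversing the shift turns the odds ratios into their mirror image, up to 1.21. The 0.57 in the last row follows from |corr(U,D)| = 0.4 with D = −0.7B + error: 0.4/0.7 = 0.57. Repeated visits and interactions are not modelled.

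**4. A real effect can be hidden.** A simpler model has dose as the only covariate, log-odds 0.5 per SD for the unmeasured factor, and correlation 0.5 with dose. With a true OR of 0.60, power is 87–90% unadjusted. Dose-adjusted, it falls to 77% or 64% if the hydrolysate arm takes 0.25 or 0.5 SD less formula.

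**5. Interactions.** These matter even when feeding is equal by arm. If benefit scales with dose and 10% take none, the arm coefficient beside an arm-by-dose term is about 0.99, because it is the effect at zero dose. The as-randomised OR is 0.66.

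**6. No hierarchy.** If either of two valid 5% tests may count, type I error lies between 5% (fully correlated) and 1 − 0.95² = 9.75% (independent).

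**The case against.** The strongest reply is that feeding should not differ by arm. Section F describes flavour masking and four-colour blinding, and section G says that feeding is disturbed as little as possible. That stands as a limit on likely size: with no arm difference, main-effect adjustment is harmless. It does not settle what the coefficient estimates, and the documents give no feeding data by arm.

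A second reply is that the section L models are explanatory. Section B already sets the assigned-group rule for the principal analyses and supplies a logrank test that matches Table 1. This is a fair reading, but section L says its models analyse the hypothesis, and no section ranks them below the logrank test. What remains is a missing hierarchy. A reader might infer that the feeding model replaces the assigned-arm test; the text does not say that.

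A reader might also infer that the plan breaks its assigned-group rule. It does not. That rule fixes group membership, which a covariate leaves unchanged. The section B sentence on baseline adjustment is conditional and does not forbid other covariates. The departure is in the estimand. The clearest contrary text is the section B rule that subgroups for treatment effects rest on baseline data, since section L treats feeding as an effect modifier.

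**Conclusion.** The point holds for the first hypothesis. As written, section L requires post-randomisation feeding variables beside the formula indicator, so the arm coefficient need not estimate the promised intention-to-treat effect. Which analysis decides is undefined. Both conclusions rest on the wording and are firm.

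The size is not firm. It runs from no bias (no arm difference), through about 5–6% false positives (0.25 SD shift), to between 5% and about 14% (0.5 SD shift in dose). A reader might take 16–39% as the expected error rate. The documents do not support that. It needs an assumed 0.5 SD arm shift in breast feeding under blinding, OR_U = 2.0 and corr(U,B) = 0.57; at corr(U,B) = 0.4 it is about 11–21%. It is a corner case and should not drive the severity.

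Nor does the point extend to the diabetes hypothesis, where time-dependent covariates are only optional. This should be fixed, but it does not invalidate the design.

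**What to change.** Name one primary analysis of the first hypothesis, by assigned formula, in the total randomised cohort. The section B logrank test fits Table 1, with the event defined as two or more autoantibodies (the section L summary variable), because autoimmunity is not defined in section B. If a section L model is preferred, name one type, generalized linear or random effect.

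Allow stratification or adjustment only for pre-specified factors fixed at or before randomisation: randomisation strata, centre, HLA risk category and gender. Take the feeding covariates and their interactions out of that test. Keep those models as labelled exploratory analyses, and state there which duration is entered.

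Record that the change was made blind to allocation and before any unblinded autoantibody analysis. This record is needed because section M allows interim autoantibody analyses, and the section O timetable places one in year 12, before the planned code opening in year 16.

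The cost is a documented change of wording, and feeding-adjusted results become exploratory. The sample size stays at 2032.

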These figures represent a conservative estimate, since they are based on the lower 95% CI (7.6%) of the observed cumulative incidence of type 1 diabetes by the age of 10 years (15.4%) in young siblings with moderate (DQB1*0302/x) and slightly increased genetic risk (DQB1*02/y), and since the high risk (DQB1*02/0302) group was not considered in the calculations. In the Pilot-2 trial the prevalence of the high risk genotype (DQB1*02/0302) was about two times higher (absolute frequency 20%) among siblings of affected children than among offspring of affected parents. If also the young siblings carrying the high risk genotype in the DiMe Study should be included in the group at risk, the lower 95% CI would be 10.6%, which should result in a recommendation of 1920 infants to be randomized for the trial. However, fewer data from non-Finnish populations are available, explaining the caution of this sample size estimate.

Table 1. Estimation of the sample size for the trial

Assumptions:									
• Confidence level:	95%								
• Power:	80%								
• Reduction in the annual frequency of multiple auto-antibodies (≥ 2 AB) by the age of 6 years	30, 40 or 50%								
• Reduction in the annual frequency of type 1 diabetes by the age of 10 years	30, 40 or 50%								

Frequency of ≥ 2 AB by the age of 6	SAMPLE SIZE								
	30% effect			40% effect			50% effect		
	I	II	III	I	II	III	I	II	III
20.7% (*02 and/or *0302)	1048	1132	1165	558	602	626	338	364	382
18.5% (*0302/x, *02/y)	1196	1294	1330	636	688	716	386	418	438
9.9% (lower 95% CI)	2252	2438	2511	1200	1300	1334	732	792	832

Frequency of type 1 diabetes by the age of 10	SAMPLE SIZE								
	30% effect			40% effect			50% effect		
	I	II	III	I	II	III	I	II	III
18.3% (*02 and/or *0302)	1330	1492	1536	706	794	824	428	482	502
15.4% (*0302/x, *02/y)	1548	1782	1834	844	948	986	512	576	606
7.6% (lower 95% CI)	3250	3658	3768	1735	1952	2032	1056	1190	1250

Column I: Mathematical sample size
Column II: Sample size corrected for a drop-out rate of 20%
Column III: Sample size corrected in addition for a 10% frequency of exclusive BF up to the age of 6 months.

RECOMMENDATION: 2032 infants and families
SCREENING TARGET: 4516 infants

[figure not shown]

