We therefore aim to randomize 2032 infants with increased genetic risk as defined in the genetic screening section (E). To achieve that number 4516 infants must be screened assuming a frequency of 45% of the genotypes conferring increased risk. The observed prevalence of risk genotypes was 50% among the 471 infants screened for the Pilot-2 trial in Finland. An enrollment scheme for the trial proper is presented in Figure 1. This flow sheet indicates that the trial requires initial access to 5806 pregnancies. This should provide at least 4936 families with consent to participate in the trial before the birth of the child provided that the consent rate is 85%. With an exclusion rate of 8.5% after birth based on the exclusion criteria approximately 4516 infants will be available for genetic screening. The observed exclusion rate in the Pilot-2 trial was 8.6%.

Infants will be recruited over a four-year period and the planned follow-up will be 6 years after the last infant has been accrued for the antibody endpoint and 10 years after the last infant is accrued for the type 1 diabetes end point. Thus, all subjects will have at least 10 years of follow-up.

Figure 1. Enrollment scheme for TRIGR

C. RECRUITMENT

Recruitment is carried out in six major centers in USA, in 18 centers in Canada, in 12 European countries, and three centers in N.S.W., Australia. A list of participating countries and recruitment estimates are presented in Appendix 1. The figures represent an estimate of eligible pregnant women available in each country. The background of these estimates is that the appraisal of the acceptance rate (best scenario 70-80%, average 60%) may vary from country to country, and accordingly the total recruitment figures are a rough estimate. According to the figures given in Appendix 1 about 65% of the participants will be recruited in North America and 35% in Europe + Australia. The recruitment will be continued past the initial 4-year period, if we have not obtained 2,032 newborn infants with increased genetic risk to the series by that time.

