An interim analysis of autoantibodies and clinical diabetes will be performed repeatedly by the Data Safety and Monitoring Board, beginning 2 years after the last subject is recruited, in order to ensure that an unexpectedly large protective effect of the intervention will be detected early. Although the follow-up will be continued, the code will be opened and the results published if either of these analyses reach sufficient statistical significance, as defined by the Data Safety and Monitoring Board.

N. ETHICAL ISSUES

Ethical approval has been obtained at each study center. Written informed consent is requested from the parents and if needed also from the child. If, during the course of this study, an alternative strategy for diabetes prevention is proven to be effective, then we will inform the families of this possibility and discuss, and likely offer its use in a rational fashion.

Detailed HLA information will be released by qualified personnel only on the request by the parents.

The diabetes associated autoantibody results will be disclosed to the families after each annual visit starting from the 6-year visit. The family will be informed by the Study Center as soon as the autoantibody results have become available.

O. TRAINING, PROJECT PLANNING AND TIME TABLE

To achieve standardization in the implementation of the study protocol, a detailed training program for the study personnel is essential. The national coordinators, nurse and nutrition coordinators participate at vital training sessions in their respective regions. We will utilize the experience gained during the second pilot study in training and informing the national investigators and their staff, when we expanded the study to Sweden, Estonia and Hungary (investigators' meetings, site visits by project staff etc.). Additional training is provided by the Monitors and other clinical team mentors to their counterparts during their visits to the centers.

1. year

- Investigator meeting at the beginning of this period to review the recruitment strategies and protocol
- Training sessions are organized for study personnel
- Recruitment and genetic screening are started
- Clinical follow-up of the children and collection of the follow-up samples are initiated
- Dietary advice, assessment and maintenance of dietary compliance of families start
- Monitoring of the implementation of the dietary intervention and the clinical follow-up

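### A significant interim result on either endpoint opens the code while diabetes is still being ascertained, and the plan does not say who may then see it

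*Combined protocol and SAP*

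**What the plan says.** The opening paragraph of the protocol states: "This is a randomized double blinded intervention study". Section L sets two hypotheses, one on antibodies and one on diabetes.

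- **Code, section M (Interim Analysis):** "Although the follow-up will be continued, the code will be opened and the results published if either of these analyses reach sufficient statistical significance". The criterion is "sufficient statistical significance, as defined by the Data Safety and Monitoring Board".
- **Code, section D (Subject Allocation):** "The randomization code will be kept by the manufacturer and it will be opened when TRIGR study is completed". No exception is given.
- **Code, section O (timetable):** the code is opened in year 16, when follow-up is completed.
- **Looks, section M:** the analysis of antibodies and diabetes "will be performed repeatedly by the Data Safety and Monitoring Board, beginning 2 years after the last subject is recruited", and its purpose is "in order to ensure that an unexpectedly large protective effect of the intervention will be detected early".
- **Looks, section O:** recruitment is completed in year 6. One interim analysis is listed, in year 12, and none in years 8-11 or 13-15.
- **Horizons, section B:** planned follow-up is "6 years after the last infant has been accrued for the antibody endpoint and 10 years after the last infant is accrued" for the diabetes endpoint.
- **Colours, section F:** two of the four colours are test formula and two are control. Each child stays on one colour, and only the manufacturer knows the key.

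**The concern.** The rule in section M is deliberate: significance on one endpoint is enough to open the code, and follow-up then goes on. If the antibody analysis alone triggers the opening, the diabetes hypothesis is still undecided. Every family knows its colour, so a released colour key is in effect individual unblinding.

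Known allocation could influence attendance, retention, symptom reporting and the use of discretionary tests. Section H leaves some room for this: one diagnostic route starts from symptoms, and an OGTT after a raised HbA1c is optional. Study feeding ends by about 8 months of age (section G), so telling a family its arm years later cannot change the child's exposure. It can only affect how diabetes is subsequently ascertained.

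The manufacturer, as key holder, also has one instruction in section D and another in section M, with no cross-reference between them.

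**Working it through.** **1. Calendar.** The timetable reproduces: recruitment ends in year 6, so the last child is 6 in year 6 + 6 = 12 and 10 in year 6 + 10 = 16. Under section M the first look falls in year 6 + 2 = 8. The year 12 entry therefore cannot be the first look, though section O does not call it the only one. The code could open up to 16 - 8 = 8 years before the timetable's date.

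**2. Check of the design inputs.** From section B: 95% confidence (taken as two-sided 0.05), 80% power, hazard ratio 0.6, 7.6% diabetes by age 10, 4-year accrual, 14 years in total. Freedman events = (1.960 + 0.842)² × (1.6/0.4)² = 7.849 × 16, rounded up to 126. With a constant hazard the mean event probability is 0.0729, so N = 126/0.0729 ≈ 1729, against 1735 in Table 1 (40% effect, column I). This is close, but it does not prove the method used.

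**3. Diagnoses still to come.** Assumptions: constant hazard λ = -ln(1 - p)/10; drop-out hazard η = -ln(0.8)/10 = 0.0223 (20% over 10 years); uniform accrual over R = 4 years (section B) to 6 years (section O). The risk p runs from 6.1%, the average of 7.6% and 0.6 × 7.6%, to 15.4%. With h = λ + η, diagnoses observed by t years after last accrual are proportional to

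E(t) = 1 - [exp(-ht) - exp(-h(R + t))]/(hR),

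and the share remaining is 1 - E(t)/E(10). Example with p = 6.1% and R = 4: h = 0.0286, E(2) = 0.1076, E(10) = 0.2902, so the remaining share is 1 - 0.371 = 63%. For diagnoses by age 10, each child's follow-up is capped at 10 years.

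| Opening at | By age 10 (Outcome Assessment) | All diagnoses to end of follow-up (sections H and L) |
|---|---|---|
| First look, last accrual + 2 years | 46-57% | 56-63% |
| Year 12, last accrual + 6 years | 12-18% | 26-30% |
| Two years before the end | 3-4% | 12-14% |

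**4. Chance that antibodies alone open the code at year 12.** This takes the plan's 40% effect on both endpoints and the lowest Table 1 frequencies (9.9% antibodies, 7.6% diabetes).

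- Expected antibody Z: 2.8016 × √(2032/1334) = 3.458 (column III) or 2.8016 × √(1735/1200) = 3.369 (column I).
- Expected diabetes Z: 2.8016 × √0.703 = 2.349 to 2.8016 × √0.74 = 2.410, using the share of all diagnoses then accrued.
- The thresholds are assumed, because the plan gives none. So is the correlation of 0.5-0.7 between the two statistics (bivariate normal).

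| Assumed two-sided threshold | Antibodies cross | Diabetes crosses | Antibodies cross, diabetes does not |
|---|---|---|---|
| 0.05 | 92-93% | 65-67% | 26-30% |
| 0.01 | 79-81% | 41-43% | 37-43% |
| 0.001 | 53-57% | 17-19% | 36-42% |

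A stricter threshold does not remove the antibody-only route. If diabetes is counted by age 10 instead (82-88% accrued at year 12) and still has 80% power at the end, its expected Z is 2.8016 × √0.82 to √0.88, or 2.54 to 2.63. The last column then falls to about 19-38% across the three thresholds.

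**The case against.** **Section M is the specific rule and section D the general one.** A reader might infer a flat contradiction. The documents do not compel that: section D, like the year 16 entry, can be read as the default, with section M as an intended exception. What stands is that neither section says so, and section M does not say who receives the code.

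**The timetable is a planning list.** A reader might infer that year 12 is the only look planned. Section O does not say that. What remains is one look schedule stated in two incompatible degrees of detail.

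**The antibody endpoint is mature at year 12.** The Outcome Assessment text makes antibodies and/or diabetes by age 6 the first-phase outcome. The antibody crossing probabilities are therefore roughly the power of a planned analysis, not a misfire. This is right, and it makes an opening on antibodies foreseeable.

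**The room for bias is small.** Glucose and HbA1c are measured annually from age 2, and OGTTs are scheduled for all at 6 and 10 years and at the last visit. The criteria are glucose thresholds, a diabetic OGTT is to be repeated, and antibody assays are blinded. Families already receive antibody results from the 6-year visit, which may itself influence attendance and testing. All of this stands; it limits the bias without excluding it.

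**Most of the exposure is past.** Last visits are in 2016-2017, which is year 16, so year 12 was about 2012-2013. Wording changed in the April 2015 version cannot alter looks held before it.

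**Type I error.** A reader might infer that repeated looks inflate the diabetes error rate. That is not shown. The thresholds are left to the Board, and the stated aim of catching an unexpectedly large effect points to a strict one. With one interim look at year 12 and a final test at 0.05, the error would be 7.5%, 5.2% or 5.0% for assumed interim thresholds of 0.05, 0.01 or 0.001.

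**Conclusion.** The point holds as a gap in protecting the blind. The plan opens the code on either endpoint during continued diabetes follow-up, and the colour scheme means this could reveal individual allocation. The number of diagnoses exposed depends on when the code opens and which diagnoses count. At year 12 it is 12-18% (by age 10) or 26-30% (all), and for an opening two years before the end, about where the April 2015 version stands, 3-4% or 12-14%. These shares rest on constant hazards, uniform accrual over 4 to 6 years and 20% drop-out. The 26-43% chance of an antibody-only opening rests in addition on the planned 40% effect on both endpoints and on assumed thresholds and correlation.

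The documents do not show that families or centers would be given the key, that any bias would be large, or that the diabetes error rate is inflated. The remedy is cheap enough to be worth making on these terms.

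**What to change.** **Section M.** State that if the Board's criterion is met before diabetes follow-up ends, only arm-level results are released, without colour names. Individual allocation and the colour key remain sealed from families, Study Centers and laboratories until diabetes follow-up is complete and the diabetes data are locked.

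**Section D.** Add the matching exception, so that the manufacturer has one instruction.

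**Section O.** Make the year 16 code-opening entry consistent with the seal, since final analysis is listed for year 17. Give one look schedule that is the same in sections M and O.

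**Cost.** Wording only. Early publication of the arm comparison remains possible and no power is lost. The downside is that families learn their allocation later. The change protects only the follow-up that remains.

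Recording the looks the Board has held and the thresholds it used would be good practice, but the point does not depend on it.
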